8.2 Summary of Methods of Data Collection

This protocol will utilize validated 21 CFR Part 11 compliant EDC software and eCOA software to collect required study data. The Investigator must ensure that data are properly recorded on each subject's eCRFs, eCOAs, and related documents. When changes or corrections are made in the eCRF, the eCOA systems will maintain an audit trail of the person making the changes, the date and time of the change and the reason for the change. Only individuals listed on the Delegation of Responsibilities Log with responsibility for eCRF completion may make entries in the eCRFs.

The Investigator or physician sub-investigator must electronically sign and date each subject's eCRF and eCOA for each timepoint completed. Individuals who will be providing electronic signatures must first submit documentation with a handwritten signature acknowledging that their electronic signature is a legally binding equivalent to their handwritten signature.

8.3 Efficacy Measures

The following assessment measures will be conducted to evaluate the long-term efficacy of sofpironium bromide gel, 5% and 15%, as indicated in the Procedures Section 7.1:

- HDSM-Ax as measured by the subject
- DLQI as measured by the subject (for subjects ≥ 17 years of age)
- Patient Global Impression Scales; Severity (PGI-S) and Change (PGI-C)

8.4 Additional Efficacy Measure

The following efficacy assessment measure will be conducted as an exploratory analysis to evaluate sofpironium bromide gel, 5% and 15%, as indicated in the Procedures Section 7.1:

• HidroQoL as measured by the subject (for subjects ≥17 years of age); only the first 100 subjects enrolled in the study will complete this assessment

9 ADVERSE EVENTS (AE) AND SERIOUS ADVERSE EVENTS (SAE)

9.1 Safety Evaluations

The Investigator is responsible for the appropriate medical care and the safety of subjects who have entered this study. The Investigator must document any AE experienced by subjects who have entered this study and report all SAEs to the Sponsor (see Section 9.3.1). Contact information for the Sponsor's medical monitor is provided on the protocol covering page.

9.2 Adverse Events

9.2.1 **Definitions of Adverse Events**

According to the Code of Federal Regulations, 21 CFR Parts 312.32 and 320.32 (IND Safety Reporting, Applicability of requirements regarding an "Investigational New Drug Application"), FDA Guidance for Industry (Investigational New Drug Safety Reporting Requirements for Human Drug and Biological Products and Safety Reporting Requirements for Bioavailability and Bioequivalence Studies in Humans) (Federal Register/Vol. 75, No. 188/September 29, 2010) and ICH E2A (Clinical Safety and Data Management: Definitions and Standards for Expedited Reporting):

CONFIDENTIAL

An adverse event (AE) means any untoward medical occurrence associated with the use of a drug in humans, whether or not considered drug related.

A suspected adverse reaction means any AE for which there is a reasonable possibility that the drug caused the AE.

The following information should be considered when determining whether or not to classify a test result, medical condition, or other incident as an adverse event:

Adverse events will be recorded from the time of informed consent.

Abnormal laboratory values should not generally be recorded as an adverse event unless an intervention is required, the laboratory abnormality results in a serious adverse event, the lab abnormality results in study termination or interruption/discontinuation of study treatment, or the lab abnormality is associated with clinical signs or symptoms. When recording an adverse event resulting from a laboratory abnormality, the resulting medical condition rather than the abnormality itself should be recorded (e.g., record "anemia" rather than "low hemoglobin").

Complications that occur in association with a protocol-mandated intervention (e.g., invasive procedures such as biopsies) should be recorded as AEs.

Whenever possible, the Investigator should group signs or symptoms that constitute a single diagnosis under a single event term. For example, cough, rhinitis, and sneezing might be grouped together as "upper respiratory tract infection". If possible, abnormal laboratory results that meet the definition of an adverse event (see above) should be reported as a clinical diagnosis rather than the abnormal value itself (e.g., "anemia" rather than "decreased blood count").

9.2.1.1 Documentation and Monitoring Adverse Events

All AEs encountered during the clinical trial following subject consent through the last dose of study drug will be recorded on the appropriate Adverse Events case report form (eCRF).

Special considerations:

Elective procedures or routinely scheduled treatments are not considered AEs. However, an untoward medical event occurring in association with a prescheduled elective procedure should be recorded as an AE.

A baseline condition is not considered an AE unless the condition worsens following study drug administration.

Death itself is not considered an AE; it is, instead, the outcome of an AE.

SAEs that are considered related (i.e., determined to be possibly, probably, or definitely related) to sofpironium bromide by the Investigator or Sponsor should be followed until the event resolves or stabilizes (see Section 9.3.1).

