2 STUDY DESIGN

This is a multicenter, randomized, open-label, Phase 3 long-term safety study of topically applied sofpironium bromide gel, 5% and 15% in subjects with axillary hyperhidrosis.

A maximum of 300 subjects, at approximately 30 clinical sites, will be enrolled to obtain approximately 150 subjects that have completed 12 months of dosing and clinical assessments.

Subjects will be randomized 1:2 to receive either sofpironium bromide gel, 5% or 15% (100 subjects dosed with 5% gel and 200 subjects dosed with 15% gel). Subjects will apply the investigational product once daily at bedtime, to their axillae for 12 months.

Vital signs and adverse events will be collected at each visit. Local tolerability assessments (including burning, itching, dryness, scaling, and erythema assessed using standardized scales) will be collected at each post-Screening visit. Blood and urine samples will be collected and analyzed at Screening and then Weeks 4, 12, 24, 36, and 48 for routine hematology, chemistry, and urinalysis parameters. Additionally, a urine pregnancy test (UPT) for females of child-bearing potential will be collected and analyzed at each visit except at Week 2 (Visit 3), Week 6 (Visit 5), and Week 52 (Visit 17). Patient-reported outcomes HDSM-Ax, PGI-S, PGI-C, and DLQI will be recorded during the study at predefined time points. HidroQoL will be recorded at baseline, Week 2, and Week 6; only the first 100 subjects enrolled in the study will complete this assessment.

A total of 17 scheduled visits will take place over approximately 52 weeks. See Section 7.1 for an events table of this study.

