5.2 Instructions for Use and Administration of Investigational Product

Investigational product kit cartons will be provided to each site and will include one individual plastic pump container per each carton. Each carton will also contain 2 applicators. An investigational plastic pump container will contain sufficient drug product for a 28-day treatment period.

Each carton will have a unique identifier number printed on the label and the pump container label will display the same unique identifier number.

Each subject will be randomized via an Interactive Response Technology (IRT) system to receive either sofpironium bromide gel, 5% or 15% to topically apply, once daily at bedtime, to each axilla using the supplied applicators for 48 consecutive weeks. Instructions on the use of the IRT system will be provided in a separate manual.

Subjects will be instructed to apply the investigational gel product to each axilla using all the gel expressed from ONE FULL ACTUATION of the pump per each axillary dose application. Each full actuation of the pump corresponds to approximately 0.551 grams for the 5% and 0.576 grams for the 15% investigational product.

The subject will apply all doses of investigational product at night, prior to going to bed using the supplied applicators. Subjects will apply their first dose of gel prior to bedtime on the night of their Baseline Visit. The subject will be instructed to continue applying the investigational product each night with the last application to occur the night before attending the end of-treatment evaluation (i.e., Week 48, Visit 16). Subjects should wash the applicator each night after dosing. Two applicators are provided in each kit to compensate for loss or damage during handling; it is not necessary to use all the applicators over the specified dosing interval.

To ensure accurate dosing, the study staff will be instructed to first prime and then weigh each pump container before dispensing to the subject. Priming is accomplished by fully pressing the pump for five (5) sequential actuations; the dispensed gel from these 5 priming actuations is considered waste and should be discarded.

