- Remind subject to bring their study medication to next visit.
- Schedule the subject to return for the next study visit.

7.2.5 *Visit 17 (End of Study)* ±5 *Days*

The following activities will be conducted:

- Perform physical exam including collection of height and weight.
- Collect vital signs (blood pressure, heart rate, respiratory rate and temperature) after subject has been seated for ≥2 minutes.
- Subject to complete HDSM-Ax assessment.
 - Subject to complete PGI-S at the end of the HDSM-Ax questionnaire.
- Perform local tolerability assessments.
- Review changes to the subject's health (AEs).
- Only if the subject did not return the study product container 12 at Visit 16, then weigh and record weight of container.
- Review concomitant medications/treatments.
- Discharge subject from the study.

7.3 **Unscheduled Visits**

If a subject is seen for an unscheduled visit, an assessment and record of AEs should be completed, as appropriate. Additional evaluations should be performed as necessary, and the appropriate CRF pages should be completed.

7.4 **Early Discontinuation of Subjects**

It is the right and duty of the Investigator to discontinue a subject's participation if the subject's health or wellbeing is threatened by continuation in the study. In the event of premature discontinuation, the Investigator should determine the primary reason for discontinuation. A subject may be discontinued from the study if any of the following circumstances occur:

- The subject experiences a serious adverse event (SAE) rendering him or her unable to continue study participation.
- The subject experiences an AE that in the opinion of the Investigator may pose a significant risk for continued participation of the subject in the study.

- The subject is unable to physically or mentally tolerate the use of the investigational product.
- An exclusion criterion becomes apparent at any time during the study; the Medical Monitor must be contacted to discuss prior to discontinuing subject participation.
- The subject is not compliant with the study procedures; the Medical Monitor must be contacted to discuss prior to discontinuing subject participation.
- The subject voluntarily withdraws from the study. When possible, identify the reason the subject withdrew consent should be documented with particular attention paid to whether an underlying AE is at cause.

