8.1.2 Adverse Events

Adverse events (AEs; See Section 9.2) will be collected for all untoward medical occurrences in a subject entered into this clinical study (e.g., signed consent), whether or not a pharmaceutical product has been administered. Any event, including local tolerability assessments (see Section 8.1.3), that requires specific treatment, results in interruption of treatment, or results in discontinuation of the subject from the study will also be reported as an AE.

Care will be taken not to introduce bias when detecting AEs and/or SAEs. Open-ended and non-leading verbal questioning of the subject is the preferred method to inquire about AE occurrence.

Appropriate questions include:

- "How are you feeling?"
- "Have you had any (other) medical problems since your last visit/contact?"
- "Have you taken any new medicines, other than those provided in this study, since your last visit/contact?"

8.1.3 *Local Tolerability Assessments*

Local tolerability assessments (See Appendix 4) will be evaluated through assessment of selected local signs and symptoms at the drug-application site. Burning, itching, dryness, scaling and erythema will be assessed using standardized 5-point scales (0-Absent to 4-Severe). These assessments are to be performed for both axillae individually. Subject assessments (burning and itching) will be made prior to the Investigator assessments (dryness, scaling and erythema).

Subject Local Tolerability Assessments: Burning and itching for each axilla will be reviewed with the subject and assessed for the previous 24 hours using the standardized scales.

Investigator Local Tolerability Assessments: Dryness, scaling, and erythema for each axilla will be assessed by the Investigator using the standardized scales.

Local tolerability signs and symptoms that result in the subject's requiring a concomitant therapy, interruption of treatment, or discontinuation from the study, will be reported as an AE.

8.1.4 *Recommendations for Dose Interruption*

To manage AEs, the Investigator may consider interruption of treatment, and/or the use of concomitant therapy. Recommended concomitant therapy includes topically applied corticosteroids. Recommendations for dose interruption are described in the table below:

Recommended Dose Interruption

Dose Interruption		
First Dose InterruptionHold treatment until the adverse event has resolved. Result dosing.		

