9.2.1.2 Assessment of Adverse Events

For each AE, the start and resolution dates, intensity, seriousness (i.e., whether the event meets the definition of an SAE (Section 9.3.1), relationship of the event to the study drug, action taken regarding study drug, and outcome of the event will be documented on the eCRF.

Intensity

The following definitions should be used to assess and grade AE intensity, including laboratory abnormalities judged to be clinically significant.

Page 38 of 74

Severity Grade		Description
Mild	1	Awareness of sign or symptom, but easily tolerated
Moderate 2		Discomfort enough to cause interference with usual activity
Severe	3	Incapacitating with inability to work or do usual activity

Note: a severe adverse event is not necessarily serious.

Relationship

The relationship of an AE to study drug should be assessed using the guidelines presented in the table below. An AE for which there has been no causal relationship reported will require follow-up to determine causality.

Degree of Certainty	Description
Definitely Related	An event that follows a reasonable temporal sequence from administration of the test article; that follows a known or expected response pattern to the test article; and that is confirmed by improvement on stopping or reducing the dosage, and reappearance of the event on repeated exposure (re-challenge).
Probably Related	An event that follows a reasonable temporal sequence from administration of the test article; that follows a known or expected response pattern to the test article; and that is confirmed by improvement on stopping or reducing the dosage of the test article; and that is unlikely to have been caused by concurrent/underlying illness or other drugs, procedures, or other causes.
Possibly Related	An event that follows a reasonable temporal sequence from administration of the test article; that follows a known or expected response pattern to the test article; but may have been caused by concurrent/underlying illness, other drug, procedure, or other causes.
Unlikely Related	An event that does not follow a reasonable temporal sequence from administration of the test article; that does not follow a known or expected response pattern to the test article, or most likely was caused by concurrent/underlying illness, other drug, procedure, or other causes, because of their known effects.
Not related	An event almost certainly caused by concurrent/underlying illness, other drug, procedure, or other causes.

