9.4 Follow-up of Adverse Events and Laboratory Test Abnormalities

AE information will be collected during the clinical trial from the time the subject signs informed consent through the final study visit. SAEs that are considered related to study drug by the Investigator or Sponsor should be followed until the events resolve or stabilize.

9.5 **Pregnancy Reporting**

Sexually active females of childbearing potential (FOCBP)* must have a negative pregnancy test prior to study enrollment and must use an effective method of contraception during the course of the study, in a manner such that risk of failure is minimized. Prior to study enrollment, FOCBP must be advised of the importance of avoiding pregnancy during trial participation and the potential risk factors for an unintentional pregnancy. The subject must sign an informed consent form documenting this discussion.

FOCBP must agree to periodic pregnancy testing and use a medically acceptable method of contraception while receiving protocol-assigned product. This includes perimenopausal women who are <12 months from their last menses. Acceptable contraceptive methods include the following:

- Abstinence for the duration of the study or where partner is sterile (e.g., vasectomy) is acceptable form of contraception;
- Hormonal contraception, including oral, injectable, or implantable methods started ≥2 months prior to screening; OR
- Two forms of non-hormonal contraception, including IUD (≥1-week status post placement), or properly used barrier methods (e.g., male or female condoms, cervical cap/diaphragm, spermicidal agents).

* FOCBP for this study includes any premenopausal female capable of becoming pregnant who has not undergone successful surgical sterilization (hysterectomy, bilateral tubal ligation [\geq 6 months prior to baseline] or bilateral oophorectomy) or is not postmenopausal (defined as amenorrhea \geq 12 consecutive months in women \geq 55 years of age).

Subjects who become sexually active or begin to have relations with a partner who is not sterile during the trial must agree to use an effective form of birth control for the duration of the study.

9.5.1 *Time period for collecting pregnancy information*

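### Protocol 9.2.1.1 ends eCRF recording of AEs at the last dose, while 9.4, the schedule and the Visit 17 procedures run to Week 52: a minor conflict, cheaply corrected

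*Protocol*

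**What the plan says.** Protocol 9.2.1.1, on documenting and monitoring AEs, states that "All AEs encountered during the clinical trial following subject consent through the last dose of study drug will be recorded" on the AE eCRF. Section 5.2 places the last application on the night before the Week 48 visit (Visit 16).

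Other parts of the same protocol run later:

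- Section 9.4: "AE information will be collected during the clinical trial from the time the subject signs informed consent through the final study visit".
- Section 2: "Vital signs and adverse events will be collected at each visit".
- The Time and Events Table (7.1) marks AEs at Visit 17 (Week 52), and the Visit 17 procedure list (7.2.5) includes an AE review.
- Sections 7 and 8.1 refer to that table for when assessments are done. Section 8.1 lists AEs first among the safety measures.

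Three further instructions give no end date. Section 8.1.2 says AEs "will be collected for all untoward medical occurrences in a subject entered into this clinical study". Section 9.1 says "The Investigator must document any AE experienced by subjects who have entered this study". Section 9.2.1.2 requires that, for each AE, the "relationship of the event to the study drug, action taken regarding study drug, and outcome of the event will be documented on the eCRF".

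On analysis, Protocol 10.3 counts as treatment-emergent any AE arising during or after the start of treatment, and plans TEAE tables at each post-baseline visit. SAP 9.4 likewise sets no cut-off at the last dose and plans tables cumulative to Week 52. SAP Section 1 says that it is based on protocol Amendment 4.

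**The concern.** AEs are the first-listed primary endpoint assessment (Protocol 10.2; SAP 2.2.1), so the period over which they reach the database should be stated once and consistently. Section 9.2.1.1 is the only sentence that attaches an end date to eCRF entry as such. Section 9.4 speaks of collection and does not mention the eCRF, and 9.2.1.2 mentions the eCRF but gives no period. A coordinator could carry out the scheduled Visit 17 review, write a new event in the source record and, relying on 9.2.1.1, not enter it.

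The events at stake are non-serious AEs that start off drug, including any that appear after stopping a year of anticholinergic treatment. If sites differed in practice, the Week-52 summaries would mix subjects with and without off-drug recording, and nothing in the tables would show it.

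**Working it through.** The plan gives no figure to reproduce. The check is a comparison of end dates and a calendar calculation.

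**End dates, nominal, with Baseline as Day 1**

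- Visit 16 (Week 48): 1 + 48 × 7 = Day 337.
- Last dose, the night before Visit 16 (5.2): Day 336. Recording under 9.2.1.1 ends here.
- Visit 17 (Week 52): 1 + 52 × 7 = Day 365. Collection under 9.4, Section 2, 7.1 and 7.2.5 ends here.

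**Gap**

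- Nominal: 365 − 336 = 29 days.
- Visit 16 on time, Visit 17 moved by ±5 days: 24 to 34 days.
- Both visits at opposite ends of their ±5-day windows: shortest (365 − 5) − (337 + 5 − 1) = 360 − 341 = 19 days; longest (365 + 5) − (337 − 5 − 1) = 370 − 331 = 39 days.
- Share of planned follow-up: 29 / 364 = 8.0%.
- For the planned 150 completers: 150 × 29 = 4,350 person-days, and 4,350 / 365.25 = 11.9 person-years. This is observation time, not a count of events.

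**Who is covered.** These figures apply to subjects who complete treatment and attend Visit 17. Section 7.4 asks early discontinuers only for the Visit 16 evaluations, so there is no fixed 29-day interval for them.

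**Which outputs could be affected**

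- An event starting in the gap is treatment-emergent under Protocol 10.3 and belongs in the TEAE tables at Visit 17. The mismatch therefore exists within Amendment 01 and does not need the SAP.
- In the SAP table list, such an event could belong in the overall summary (14.3.1.1) and in the Week-52 set (14.3.1.10.1 to .16). The exceptions are the dose-interruption and dose-modification tables (.7 to .10), which cannot gain events that start after dosing has ended.
- Tables through Week 48 could lose only events starting between the last dose and Visit 16, about one day.
- SAEs are covered separately: 9.3 requires reporting of any SAE after study drug administration, without a last-dose limit. Scored local tolerability is scheduled at Visit 17 in its own right.

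**Number of missed events.** This cannot be computed. The documents give no off-drug AE rate and do not show which sentence sites followed.

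**The case against.** The strongest reply is that the protocol as a whole points one way. Sections 7 and 8.1 assign the timing of AE assessment to the Time and Events Table, which marks Visit 17. Section 8.2 requires data to be properly recorded on eCRFs and each completed timepoint to be signed. Sections 9.1 and 9.2.1.2 ask for every AE to be documented. To lose an event, a site would have to do the Visit 17 review and then decline to enter what it found, against all of this. That largely stands, and it is why the point is minor. It does not remove the conflict: the schedule governs when AEs are assessed, and no sentence expressly sets aside the last-dose limit on eCRF entry.

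The second reply is that Amendment 01 was superseded. The SAP follows Amendment 4, and some text appears to have been tidied in between. For example, the laboratory weeks in Protocol Section 2 (4, 12, 24, 36, 48) differ from those in SAP 2.3 (6, 24, 48), and SAP Section 13 does not list this as a change from the protocol. But SAP Section 13 also shows that the synopsis baseline definition was still inconsistent, so correction of 9.2.1.1 cannot be assumed. Its status in the operative protocol is unknown.

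A reader might also infer that 9.2.1.2 contradicts 9.2.1.1. It does not: it lists what to document for each AE and has no time window. Nor does 9.2.1.1 contain the word *only*; the limit comes from the end date that it names.

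**Conclusion.** The inconsistency is real within Amendment 01: 9.2.1.1 is out of line with 9.4, the schedule and the Visit 17 procedures, and does not fit the tabulation planned in 10.3. Its possible effect is under-reporting of non-serious AEs that start in a window of about 29 days (19 to 39), or 8.0% of planned follow-up, for subjects who complete treatment and attend Visit 17. The effect arises only if a site followed 9.2.1.1 literally. Severity is minor; no hypothesis test or formal sample-size calculation depends on it.

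Three stronger inferences are not supported:

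- That off-drug AEs were lost. Nothing in the documents shows that any site stopped recording at the last dose.
- That the SAP contradicts its own protocol. The SAP follows Amendment 4, so a comparison with Amendment 01 crosses versions. The established conflict is internal to Amendment 01.
- That the number of Week-52 tables measures the impact. Their categories overlap and most are repeated for two denominators, so one event can appear in many of them.

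The conclusion assumes nominal visit timing within the stated windows and dosing through the night before Visit 16.

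**What to change.** If the operative amendment has not already done so, change the end point in 9.2.1.1 from the last dose to the final study visit (Week 52) and cross-reference 9.4. Before database lock, check that AEs found at Visit 17 were entered on the eCRF; where they were not, footnote the Week-52 AE tables to say so.

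The cost is one phrase in the protocol and one data-management check. No visit, procedure or analysis is added.
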